Indicate which of the following are employed as a part of screening or main study consent procedures

✓ Consent Form

Persons designated to discuss and document consent

Select the names of persons designated to obtain consent/assent

- [name]
- [name], MD
- [name]
- [name]
- [name], MD
- [name], MD
- [name], MD
- [name], MD
- [name]. MD
- [name]
- [name], MD

Type in the name(s) not found in the above list

Study Procedures

Describe the procedures required for this study

Potential subjects will undergo a screening visit which will include a demographics questionnaire, medical history, physical examination, psychiatric evaluation, laboratory testing, and electrocardiogram. The MINI International Neuropsychiatric Interview (MINI) will be conducted to determine current DSM-5 diagnoses. Eligible participants will be offered the opportunity to participate in the research treatment study, using the IRB-approved consent form obtained by the research psychiatrist.

This is an open-label pilot trial to evaluate the safety and tolerability of lofexidine in the management of opioid withdrawal symptoms while initiating outpatient treatment with naltrexone. The initiation procedure will be a flexible detoxification lasting 2 to 10 days concluding with the injection of XR-Naltrexone (Vivitrol). Lofexidine will be fixed-flexible dosing started on day 1 with maximum dose being three 0.18mg tablets taken orally 4 times daily at approximately 4-to 6-hour intervals. Lofexidine treatment will continue throughout the detoxification, up to 10 days, and will be discontinued with a gradual dose reduction over 2 to 4 days (Table 2). Precipitated withdrawal symptoms are treated with lofexidine, clonazepam, and other adjuvant medications as detailed below.

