The study will be entirely outpatient. Upon study entry, participants will begin clinic visits at the Substance Treatment and Research Service (STARS) clinic. After the detoxification period (2-10 days) where participants will attend the clinic daily, participants will then attend the clinic twice per week for the next 4 weeks and then once per week for the last 4 weeks. All participants will visit the clinic weekly to provide urine toxicology, report on adverse events, and complete additional assessments. All participants will also receive medical management, a medication adherence focused psychosocial intervention that facilitates compliance with study medication and other study procedures, and promotes abstinence from opioids and other substances.

Detoxification and Induction onto Injectable Naltrexone: The detoxification-naltrexone induction will be performed at the STARS outpatient research clinic, which is outfitted with a detoxification suite. After study consent and prior to initiating any study procedures, a urine will be collected and tested for pregnancy. A negative urine pregnancy is required at admission as detoxification and naltrexone treatment would not be recommended during pregnancy.

Participants come to the clinic daily for safety assessments, clinical monitoring, and management of withdrawal. Patients will be seen at the clinic preferably in the morning on Day 1 to initiate the lofexidine-naltrexone procedure. On Study Day 1, following the consent procedure, participants will start lofexidine and will be instructed to begin to abstain from opioids. Vital signs will be checked post 1 hour of initial lofexidine dose to see if there is an effect on blood pressure. Participants will continue to receive lofexidine 0.18mg #3 QID (approximately 9am, 1pm, 5pm, 10pm). Administration of lofexidine is withheld in case of dizziness or lightheadedness complaints, low blood pressure (SBP < 90 or DBP < 60), or orthostatic blood pressure changes (from lying down to standing up drop of SBP \geq 20 mmHg, DBP \geq 10 mmHg). If there are

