changes in blood pressure or reported dizziness/lightheadedness we will hold off on lofexidine dosing, hydrate the participant and repeat blood pressure after 30 to 60 minutes to determine how long the lofexidine dose will be held. If vital signs and reported side effects return to normal ranges lofexidine dose will be continued as per protocol. If vital signs and reported side effects remain lofexidine medication will be held until the next study visit. We will counsel all participants in the importance for adequate oral hydration during the consent process and throughout the study.

Participants will be monitored by clinical staff frequently, with vital signs checks and withdrawal assessments. Starting day 1 participants will be sent home with ancillary medications (clonazepam, zolpidem) and will be instructed that they may use ancillary medication if needed.

Ancillary medications: A standing order of additional medication targeting withdrawal symptoms will be available to patients and will include clonazepam 1 mg tid and zolpidem 10 mg QHS. Ancillary medications will be offered daily during the induction week and will include clonazepam to reduce anxiety and dysphoria, and zolpidem for insomnia. Participants will be provided take-home doses of ancillary medications in small doses and on a tapering schedule for two weeks (after the detoxification week) to alleviate any protracted opioid withdrawal. Additional doses will be offered as clinically determined for participants experiencing continued withdrawal symptoms.

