This outpatient detoxification/naltrexone induction medication protocol is outlined in Table 2, below. Evaluation of withdrawal severity (COWS) and vital signs, will be obtained at least twice per day (at the beginning and end of their study visit). Additional COWS can be administered as per clinical judgment of the study physician and nurse practitioner.

For female participants, a urine pregnancy test will be obtained on the day of each vivitrol administration. If at any time during the study a female participant has a positive urine pregnancy test, this will be reported to the IRB and the study sponsor, US WorldMeds and the participant will be discontinued from the study. We will follow our study discontinuation procedure as outlined below to transition these individuals to a treatment program in the community.

Outpatient Treatment Post-Detoxification

Study Visits

Participants will have two weekly clinic visits during the first month of treatment and one weekly visit during the second month. At each visit the patient meets with the research assistant to complete research ratings, including self-report of withdrawal, mood, and drug use. The patient provides a urine sample under observation by a staff member at each visit. The sample is tested immediately for opioids. Vital signs are also taken. Once a week participant will meet with a study psychiatrist for safety and tolerability evaluation, along with medical management therapy.

Participants may come to the clinic to be seen as frequently as needed. In particular, any participant who is experiencing protracted opioid withdrawal will be offered clinical contact on a frequent, even daily, basis. For clinical matters arising in the evenings or on weekends, participants will have access to the 24-hour emergency telephone service, staffed by physicians familiar with this protocol who can address patients' concerns.

Outpatient medications

On the day after the XR-naltrexone injection participants will receive tapering doses of lofexidine for 2-4 days. During the subsequent 8-week course of outpatient treatment, patients receive additional injection of Vivitrol 380 mg, at week 4.

Medication Management

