If a patient misses scheduled injection of Vivitrol and resumes regular opiate use, then receiving injectable naltrexone will precipitate opiate withdrawal, which may be quite severe in proportion to the time since the last injection and the level of opiate dependence. The physician will evaluate the patient and perform a naloxone challenge test to determine whether or not naltrexone can be safely resumed. If the naloxone challenge is positive (withdrawal is precipitated), then the patient will be removed from the study and offered another treatment options such as agonist maintenance (buprenorphine or methadone) according to clinical judgment and the patient's preferences (please see Study Discontinuation Procedure in Study Procedures section for full details).

Self-administration of large doses of opiates may over-ride the blockade produced by naltrexone resulting in opiate over dosage with its attendant risks including respiratory depression and death. Patients will be warned of the severe danger of using opiates, including trying to over-ride the blockade. Also patients who have stopped naltrexone and resume opiates will not be tolerant initially, so that the quantities of opiates self administered prior to treatment, when they were tolerant, may be quite dangerous in the non-tolerant state. Patients will be warned of this. Patients who self-administer opiates to the point of somnolence or stupor will be removed from the trial and referred to inpatient treatment in combination with medication (methadone, buprenorphine, Vivitrol).

In the event of a medical emergency requiring opiate analgesia, a patient on naltrexone will require higher doses of opiates than normally administered. Patients will be informed of this and will be given a naltrexone medication card to carry in their wallet.

Side-Effects and Risks of Lofexidine

Treatment with lofexidine may cause hypotension, dizziness, dry mouth, and bradycardia. Participants will be encouraged to hydrate orally when taking lofexidine. Blood pressure will be checked at each clinic visit. Lofexidine will be held if the patient's blood pressure falls below 90/60. Additional risks include syncope.

rebound hypertension and QT prolongation. ECG will be obtained during the screening and patients at risk for QT prolongation (e.g., moderate to severe renal or hepatic insufficiency) will be excluded.

Pregnancy:

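### Only the first lofexidine dose has a blood-pressure check timed to it, evening doses are followed by no reading until the next visit, and the SAP does not tabulate blood pressure, so hypotension may be understated

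*Combined protocol and SAP*

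**What the plan says.** Specific Aims and Hypotheses gives a single aim, lofexidine's safety and tolerability. The Background says hypotension and bradycardia limited clonidine dosing in earlier trials, and Side-Effects and Risks of Lofexidine lists hypotension first.

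**Dosing and setting** (Study Procedures). "The study will be entirely outpatient". After the initial dose, "Participants will continue to receive lofexidine 0.18mg #3 QID (approximately 9am, 1pm, 5pm, 10pm". On duration: "Lofexidine treatment will continue throughout the detoxification, up to 10 days, and will be discontinued with a gradual dose reduction over 2 to 4 days".

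**Blood pressure.** Detoxification and Induction onto Injectable Naltrexone has one check tied to a dose: "Vital signs will be checked post 1 hour of initial lofexidine dose to see if there is an effect on blood pressure". At the end of Naloxone challenge and Vivitrol injection, COWS and vital signs "will be obtained at least twice per day (at the beginning and end of their study visit". Study Procedures also promises frequent vital-sign checks by clinical staff. The lofexidine risk section says "Blood pressure will be checked at each clinic visit".

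**Hold rule.** Study Procedures withholds lofexidine for dizziness or lightheadedness, for systolic pressure under 90 or diastolic under 60, or for an orthostatic fall of at least 20 systolic or 10 diastolic. Pressure is repeated after 30 to 60 minutes. If findings persist, the drug is held until the next visit. The risk section gives only a fall below 90/60.

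**Take-home drugs.** "Starting day 1 participants will be sent home with ancillary medications (clonazepam, zolpidem". Lofexidine is not named there.

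**Capture and analysis.** At visits, SAFTEE asks about side effects since the previous one. The SAP (Overview of Data Analytic Plan) tabulates adverse-event frequency and names no vital-sign, hypotension or hold outcome.

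**The concern.** On Day 1 the protocol itself treats a reading one hour after dosing as the way to see an effect on blood pressure. After that, no reading is placed relative to a dose, and nothing visible asks for the dose time beside a reading. A pressure taken one hour after a dose and one taken many hours later would look the same in the data.

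The 10pm dose, and the 5pm dose unless the visit runs past it, are taken away from the clinic with no measurement afterwards. A drop that causes no symptoms, or appears only on standing, could pass unrecorded.

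The readings that are taken may not reach the results either, because the SAP reports adverse events and not the blood-pressure data. At stake is whether a low count of hypotension in this pilot means that lofexidine was well tolerated, or that pressure was seldom measured when a drop was likely.

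**Working it through.** The plan states no hypotension rate, no detection probability and no sample-size calculation for this outcome, so there is no figure to reproduce.

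**1. Doses and readings.** Inputs: 4 doses per day at about 9am, 1pm, 5pm and 10pm; 2 to 10 days; at least 2 vital-sign sets per daily visit. Doses = 4 × days; timed share = 1 ÷ doses; minimum sets = 2 × days. Dose counts are maxima, since dosing is described as fixed-flexible and doses may be held.

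| Days | Doses | Timed to a dose | Minimum vital-sign sets |
|---|---|---|---|
| 2 | 8 | 1 (12.5%) | 4 |
| 7 | 28 | 1 (3.6%) | 14 |
| 10 | 40 | 1 (2.5%) | 20 |

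**2. Doses outside the clinic.** Visit length is not given. Assuming 1, 2 or 3 of the 4 daily doses fall within the visit, (4 − 1) × 10 = 30, (4 − 2) × 10 = 20 or (4 − 3) × 10 = 10 of the 40 doses fall outside it.

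**3. Gap after the last dose.** The intervals between doses are 4, 4, 5 and 11 hours. The reading after a 10pm dose is the next visit's. If that visit starts at 9am, the gap is 11 hours. The text prefers a morning visit for Day 1 and gives no clock time for later days, so this is an example and not a property of the plan.

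**4. Per dose and per participant.** Assume a 10-day induction, an independent chance q of a drop after each dose, every in-clinic drop seen and no home drop seen. The chance of at least one recorded drop is 1 − (1 − q)^k, with k doses observed.
- q = 10%: 1 − 0.9^10 = 65%; 1 − 0.9^20 = 88%; 1 − 0.9^40 = 98.5%.
- q = 5%: 1 − 0.95^10 = 40%; 1 − 0.95^20 = 64%; 1 − 0.95^40 = 87%.

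Observing a quarter or half of the doses then identifies about 66% (65 ÷ 98.5) or 89% (88 ÷ 98.5) of affected participants at q = 10%, and about 46% (40 ÷ 87) or 74% (64 ÷ 87) at q = 5%. The loss per participant is smaller than the loss per dose, because visits repeat.

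**5. Effect on the reported count.** Take the 20 planned participants, a true proportion p affected and a share s of those recorded (both assumed). Expected count = 20ps; P(none recorded) = (1 − ps)^20.

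| p | s | Expected recorded | Truly affected | P(none recorded) |
|---|---|---|---|---|
| 20% | 50% | 2 | 4 | 0.90^20 = 12.2% |
| 20% | 75% | 3 | 4 | 0.85^20 = 3.9% |
| 40% | 50% | 4 | 8 | 0.80^20 = 1.2% |
| 40% | 75% | 6 | 8 | 0.70^20 = 0.1% |

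With s = 100% nothing is understated. The documents give neither p nor s, so this shows how the result could move. It does not estimate the bias.

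**6. After induction.** Outpatient medications starts a 2 to 4 day taper the day after the injection, when scheduled visits fall to twice a week. Some taper days may have no scheduled reading.

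**The case against.** The strongest reply is that monitoring is far from absent. Visits are daily during detoxification, with at least 20 vital-sign sets over 10 days, further checks in clinic, and an hour of vital-sign monitoring on the day of a naloxone challenge. SAFTEE recovers symptomatic episodes between visits. Missed doses are queried weekly and pills are counted. Table 2 and the assessments table are uploads that cannot be seen here, and either could hold dose-linked timing or take-home instructions. This is also a 20-person open-label pilot.

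All of that stands, and it rules out several stronger readings that a reader might infer:
- *That the hold rule cannot reach home doses.* A finding that persists in clinic holds lofexidine until the next visit, which covers the doses in between, and one trigger is a symptom that needs no cuff. What remains is a drop that first arises after a home dose: nothing visible measures it or says how the rule then applies.
- *That readings are mostly at trough.* No visit times after Day 1 support this.
- *That 2.5% of dosing is monitored, or that at most a quarter to a half of drops can be seen.* The first ignores the visit-tied sets. The second is a per-dose ceiling under assumptions, and step 4 shows that it does not carry over to participants.

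None of this supplies the time since dose for a reading, a measurement after evening doses, or a blood-pressure summary in the SAP.

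**Conclusion.** The concern holds in limited form. In the visible text, one reading is timed to a dose, no later reading carries a dose time, and at least the 10pm dose is followed by no measurement until the next visit. The SAP does not report the blood-pressure data collected. Asymptomatic and orthostatic drops after home doses may therefore be missed, and the trial may understate hypotension.

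It would go too far to say that the trial will understate it. Symptomatic episodes can be recalled, and in-clinic readings are repeated daily. The size of any understatement cannot be fixed: in the illustration it runs from none, if every affected participant is recorded, to half of the affected participants if s is 50%. The conclusion rests on the visible text and on the inference that a 10pm dose in an outpatient study is taken at home. It would change if Table 2 or the assessments table already links readings to doses.

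**What to change.** First check Table 2 and the assessments table. If they do not settle the matter:

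1. **Protocol, Study Procedures** (the induction text and the vital-signs sentence at the end of the naloxone challenge section). Record the time of the last lofexidine dose with every vital-sign set. Where a scheduled dose already falls within a visit, take one of the existing readings about one hour after it, as is done on Day 1.
2. **SAP, Overview of Data Analytic Plan.** Tabulate per participant, with exact 95% confidence intervals, low blood pressure and orthostatic change at the thresholds already in Study Procedures, and dose holds. Present these by time since last dose. State that blood pressure after home doses is unobserved, since a confidence interval covers sampling error and not missed readings.
3. **Reconcile** Study Procedures with Side-Effects and Risks of Lofexidine. The first gives symptom, low-pressure and orthostatic triggers, the second only a fall below 90/60. State whether lofexidine is dispensed to take home and how the hold applies to home doses. The investigators must settle these points; no clinical rule is proposed here.

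The cost is protocol and SAP wording, one extra data field, and up to one more hour in clinic at some induction visits. No extra visits are needed. Dose times that are not recorded cannot be recovered reliably later.

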All participants will receive medical management once weekly during the post-induction phase, a medication adherence focused psychosocial intervention that facilitates compliance with study medication and other study procedures, and promotes abstinence from opioids and other substances. Overdose prevention education including a naloxone kit will be given to each patient.

Procedures for missed doses of XR-naltrexone

If a patient misses a scheduled second injection and takes an opioid during at least two of the seven days following the date of the scheduled injection, relapse will be suspected (the participant reports recent opioid use, and/or has a positive UDS for opioids), a naloxone challenge may be performed, if appropriate, using 0.8 mg naloxone IM. The patient is followed clinically and withdrawal symptoms are assessed over the next hour. If the challenge is negative, the administration of vivitrol will be resumed. However, because there are blood levels and partial blockade beyond four weeks after the initial administration of vivitrol, vulnerability to relapse may be more gradual, and the instance of mild or equivocal reactions to the naloxone challenge

more common. In this instance, a second challenge within 72 hours, will be attempted, and if tolerated, the next injection of Vivitrol can be given. Patients who fail two consecutive naloxone challenges are considered to have relapsed and are referred for inpatient treatment combined with medication or agonist maintenance, as deemed clinically appropriate and in accordance with the patient's wishes. Patients who fail two negative naloxone challenges will be given a week supply of buprenorphine and will be provided with referrals. Buprenorphine is not included in the standard detoxification procedure for this study, but introduced as bridge medication. We will work with patients and make every effort to stabilize patients on buprenorphine at the clinic until a referral is secure. Patients will be at risk of overdose if they are not stabilized on one of the effective medications. Thus we will work hard with them to secure placement. Please see our study discontinuation procedure below.

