Missing a scheduled XR-naltrexone injection is the most important threat to the success of Vivitrol maintenance. In the event of a patient missing a scheduled injection, staff will immediately attempt to contact the patient to re-establish commitment to the naltrexone treatment and reschedule the injection within a 24-48 hour period. If the patient cannot attend the treatment center within a two-day time-frame, or cannot be located, the treatment team will use previously obtained locator information in an effort to locate the patient through emergency contacts and try to get them in for a visit.

Study Discontinuation Procedure:

Participants who had no response to naltrexone treatment, such as those who continued using opioids while on naltrexone as well as those who stopped taking naltrexone (missed scheduled injections) and/or resumed opioids after missing naltrexone, are considered to be at very high risk of a full relapse and overdose. We will work with patients and make every effort to stabilize patients on buprenorphine at the clinic until a referral is secure. These individuals will be immediately directed toward either inpatient treatment such as residential treatment in combination with medication (methadone, buprenorphine, and/or Vivitrol), or toward agonist maintenance with either buprenorphine/naloxone or methadone. Methadone maintenance treatment is widely available in the community; however, access to buprenorphine treatment is more restricted.

In order to minimize the risk of relapse due to the lack of access to the medication and the gap between treatment providers we would like to offer 2-week supply buprenorphine/naloxone 8mg to participants who are in the process of being referred out to either inpatient treatment or an agonist maintenance program. We will continue to provide additional support including frequent, daily if needed visits at our clinic for a maximum of 2 weeks.

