Treatment to be provided at the end of the study

All participants who remain active in treatment will have an End-of-Study visit, within a week of the final study day (approximately 28 days after second XR-NTX injection), during which final ratings measures, and toxicology will be obtained. At the conclusion of the protocol, the participants will be offered supportive therapy for at least one additional month or until an appropriate referral for on-going treatment is made. If the patient is interested to continue on XR-NTX, we will try to work with the patient's insurance to provide coverage to continue XR-NTX. Most insurance plans cover Vivitrol, and we have developed a network of providers who we have referred patients to. If the patient is unable to find a provider to administer injection but we were able to secure the medication through patient's insurance and the patient is at risk to become unblocked we will administer the injection.

Participants who had no response to naltrexone treatment, such as those who continued using opioids while on naltrexone as well as those who stopped taking naltrexone (missed scheduled injections) and/or resumed opioids after missing naltrexone, are considered to be at very high risk of a full relapse and overdose. These individuals will be immediately directed toward either inpatient treatment such as residential treatment in combination with medication (methadone, buprenorphine, Vivitrol), or toward agonist maintenance with either buprenorphine/naloxone or methadone. Methadone maintenance treatment is widely available in the community; however, access to buprenorphine treatment is more restricted.

We will use buprenorphine as a bridge if a participant cannot or does not want to take vivitrol. In order to minimize the risk of relapse due to the lack of access to the medication and the gap between treatment providers we would will offer a 2-week supply of buprenorphine/naloxone, up to 24mg per day (as per clinical judgment) to participants who are in the process of being referred out to either inpatient treatment or an agonist maintenance program.

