Buprenorphine has been associated with adverse effects typical of opioid agonist drugs (e.g. sedation, constipation, insomnia, headache, nausea), although as a partial agonist such effects are typically less pronounced than they would be with a full agonist. The most common adverse event associated with the sublingual administration is oral hypoesthesia. Other adverse events were constipation, headache, intoxication, disturbance in attention, palpitations, insomnia, sweating, and blurred vision. Buprenorphine by itself has little tendency to suppress respiration and is associated with a low risk of overdose, a safety advantage. However, there is a risk of overdose if buprenorphine is combined with sedative drugs such as benzodiazepines or alcohol, analogous to the risk of combining such sedating medications with a full agonist like methadone. As a partial agonist, buprenorphine can precipitate an acute opioid withdrawal reaction if taken within 12-18 hours of another short-acting full opioid agonist, or within 48-72 hours of a longer-acting full opioid such as methadone. Study physicians have extensive experience, in both research and clinical settings, in administering buprenorphine and in the management of opioid withdrawal symptoms.

Side Effects of Extended-Release (XR), Injectable Naltrexone: The most common side effect associated with injectable naltrexone is injection site reaction. XR-naltrexone is administered as a gluteal intramuscular injection and injection site reactions, mostly pain, and occur in approximately 5% of patients in opioid treatment studies. These reactions are generally mild and include pain, tenderness, indurations, bruising, pruritus and swelling. Generally, these reactions last 1-3 days. Rare skin reactions at the site of the injection have been reported, including sterile abscesses, which may relate to inadvertent injection into fatty tissue, rather than muscle. Patients will be informed of this risk, and baseline physical evaluation will include examination of the buttock for excessive adiposity. If a patient is examined by a physician and found to have an abscess, necrosis, cellulitis or extensive swelling, an appropriate surgical referral will be made. In addition, Vivitrol could result in withdrawal symptoms at the first dose. Study physicians will inform participants of this risk prior to receiving the injection.

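### The buprenorphine bridge for participants leaving naltrexone has two conflicting supply lengths, an 8 mg amount without a time unit, and a trigger that cannot occur as written

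*Combined protocol and SAP*

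**What the plan says.** Four parts of the protocol describe the bridge, and others set the rules that lead to it.

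- **Study Procedures, Procedures for missed doses of XR-naltrexone.** The setting is stated at the start: "If a patient misses a scheduled second injection and takes an opioid during at least two of the seven days following the date". A naloxone challenge may follow. "If the challenge is negative, the administration of vivitrol will be resumed". After a mild or equivocal reaction, a second challenge is attempted within 72 hours. Then: "Patients who fail two consecutive naloxone challenges are considered to have relapsed and are referred for inpatient treatment combined with medication or agonist maintenance". The next sentence reads: "Patients who fail two negative naloxone challenges will be given a week supply of buprenorphine and will be provided with referrals". The paragraph closes by sending the reader to the discontinuation procedure.
- **Study Procedures, Study Discontinuation Procedure.** This covers people who keep using opioids on naltrexone and people who miss injections or go back to opioids afterwards. For those being referred onward: "we would like to offer 2-week supply buprenorphine/naloxone 8mg to participants".
- **Treatment to be provided at the end of the study.** This repeats the same description of the population, says that the bridge is for anyone unable or unwilling to take Vivitrol, and offers a "2-week supply of buprenorphine/naloxone, up to 24mg per day (as per clinical judgment". The buprenorphine paragraph under Risks repeats that offer.
- **Risks, side effects of injectable naltrexone.** One positive challenge, meaning that withdrawal is precipitated, leads to removal from the study.
- **Procedures for minimizing risks.** The missed-dose text appears again with the second challenge and the two-failure rule, but without the one-week supply.
- **Criteria for Early Discontinuation.** Not passing a challenge within the 10-day induction is the first criterion. The section refers to the Study Discontinuation Procedure.

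**The concern.** These are operating instructions for dispensing a take-home controlled drug to people whom the protocol itself describes as being at very high risk of relapse and overdose. If the sections disagree, the quantity a participant takes home, and the point at which the participant leaves naltrexone, depend on which page staff happen to read. A trigger that cannot be met leaves the one-week instruction without a defined population. Participants treated under different readings would also be handled differently within one small pilot, in which 20 are to be enrolled to obtain 10 completers.

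**Working it through.** No statistical figure is involved. The check sets the bridge statements side by side, asks whether they apply to the same person, and multiplies days by mg.

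**1. The statements**

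| Section | Who | Duration | Product and amount |
|---|---|---|---|
| Missed doses of XR-naltrexone | Missed second injection, two challenges | 7 days | Buprenorphine, no dose |
| Study Discontinuation Procedure | Non-response, missed injection or return to opioids; being referred out | 14 days | Buprenorphine/naloxone 8 mg, not stated as per day or per unit |
| Treatment at end of study; Risks (buprenorphine) | Unable or unwilling to take Vivitrol; being referred out | 14 days | Buprenorphine/naloxone, up to 24 mg per day |

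**2. Do they apply to the same person?** Take a participant who misses the second injection, resumes opioids and fails two challenges. The missed-dose procedure covers this person directly and passes the person to the discontinuation procedure. That procedure names missed injections and return to opioids among its cases. The end-of-study section repeats that description, and this person can no longer take Vivitrol. All of the statements therefore apply.

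**3. Duration.** 14 / 7 = 2. The difference is 2-fold and rests on no assumption.

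**4. Amount**
- One-week statement: cannot be computed, because no dose is given.
- Discontinuation procedure, assuming that 8 mg is a daily dose: 14 x 8 = 112 mg.
- End-of-study and Risks sections: at most 14 x 24 = 336 mg.
- On that assumption the ratio is 336 / 112 = 3. If 8 mg is a unit strength, the 112 mg figure falls away and the two-week statements need not differ on dose.

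**5. The trigger.** In the missed-dose paragraph a negative challenge means that Vivitrol goes ahead. The Risks section uses positive for precipitated withdrawal. A participant who has had two negative challenges has passed twice, so nobody can meet the one-week condition as worded. The sentence just before it requires two consecutive failures, which is coherent.

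**6. How many challenges?** The Risks section removes a participant after one positive result. Both missed-dose texts allow a second challenge after a mild or equivocal reaction and declare relapse after two failures. No section says whether a mild reaction counts as positive, so the same result can lead to removal or to a repeat test.

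**7. Failed or refused induction.** This route runs from Criteria for Early Discontinuation to the Study Discontinuation Procedure, or through the end-of-study statement. Both give two weeks. The one-week sentence does not apply here.

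**The case against.** Much can be said for the text as it stands.

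- **The trigger looks like a one-word slip.** The intended meaning probably sits in the preceding sentence, and the faulty wording governs only the one-week supply. That is fair, but this is the sentence that dispenses the drug, so it still has to be corrected.
- **One week could be a first instalment.** The same paragraph promises to work with patients until a referral is secured. Nothing in the text links the two supply lengths in that way, so the conflict stands as written.
- **The one-or-two-challenge difference may reconcile.** A clear reaction could mean removal and an equivocal one a repeat test. That is a possible reading, but it needs a definition that the protocol does not give.
- **A 3-fold dose contradiction is not established.** A reader might infer one from 8 mg and 24 mg. The 8 mg has no time unit, and even as a daily dose it lies within a ceiling of 24 mg left to clinical judgment.
- **Different products are not established either.** The end-of-study section itself says buprenorphine and then specifies the combination, so the shorter name is probably shorthand.
- **Overlap with take-home clonazepam is not general.** The Risks section warns that "there is a risk of overdose if buprenorphine is combined with sedative drugs such as benzodiazepines or alcohol", and clonazepam goes home "on a tapering schedule for two weeks (after the detoxification week". The second injection is due at week 4, by when the scheduled taper should normally have ended, unless discretionary extra doses are given. Overlap is plausible mainly after a failed or refused induction, and there the one-week sentence does not apply.
- **The number affected is unknown.** Enrolling 20 for 10 completers implies at most 20 - 10 = 10 projected non-completers. The protocol does not say why they would leave, and some may be lost to contact and receive no bridge.

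**Conclusion.** The inconsistency is real and worth correcting, within limits. Two elements are certain: one week against two weeks for the same participant after a missed second injection, and a trigger that contradicts its own paragraph. Two are ambiguities: what 8 mg refers to (112 mg against up to 336 mg over 14 days only if it is daily), and whether one positive challenge or two failures end naltrexone treatment.

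A reader might infer that a failed or refused induction meets three rival bridge rules. The documents do not support that, because both statements that reach those participants give two weeks. A reader might also infer that half the sample is exposed to the conflict. Ten is only a ceiling on non-completers, and those who reach the one-week sentence must first have had an injection and then missed the second.

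The consequence is for consistent and safe handling of participants. The COWS model and the induction proportion in the Overview of Data Analytic Plan do not depend on the bridge. Correction is recommended on safety and consistency grounds.

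**What to change.** Write one bridge statement giving trigger, product, amount with its unit (per day or per dosage unit) and duration. Use it identically in the missed-dose procedure, the Study Discontinuation Procedure, the end-of-study section and the Risks section.

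In the same amendment:

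- Bring the wording of the one-week trigger into line with the protocol's own use of positive and negative challenges.
- Reconcile the single-challenge removal rule under Risks with the two missed-dose texts, and say how a mild or equivocal reaction is classed.
- For participants who fail or refuse induction, check the statement against the protocol's own warning on sedatives, since take-home clonazepam may still be in use.
- Check the consent form, which is not among the documents reviewed here, against the reconciled text.

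Which dose, duration and challenge rule apply is for the investigators to decide. The cost is a wording amendment and a consent check, with no added visits, participants or analyses.
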